1.4.2.9 PRO 140_CD02 Study

PRO 140_CD02 study (double blind, placebo controlled, 50 subjects, multi-center) seeks to evaluate the efficacy, safety, and tolerability of PRO 140 in combination with existing ART (failing regimen) for one week and Optimized Background Therapy (OBT) for 24 weeks in patients infected with HIV-1. The study population includes 50 treatment-experienced HIV-infected adult patients with CCR5-tropic virus who demonstrates evidence of HIV-1 replication despite ongoing antiretroviral therapy with documented history of genotypic or phenotypic resistance to at least one ART drug within two drug classes.

In double-blind treatment period, virally non-suppressed subjects will be randomized and treated with either PRO 140 or Placebo in combination with the failing ART regimen for 7 days. The primary efficacy endpoint is proportion of participants with \geq 0.5 log₁₀ reduction in HIV-1 RNA viral load from baseline at the end of the 7 day functional monotherapy period.

During the 24-week open-label period, all subjects will receive PRO 140 along with OBT.

1.4.2.10 PRO 140_CD02 Extension study

PRO 140_CD02 Extension study (open label, 50 subjects, multi-center) seeks to evaluate the long term efficacy, safety and tolerability of PRO 140 weekly injection in combination with Optimized Background Therapy (OBT) in patients infected with HIV-1. The study population includes 50 treatment-experienced HIV-infected adult patients with CCR5-tropic virus who successfully completed PRO 140_CD02 study and continue to demonstrate HIV-1 viral suppression.

This clinical study is currently ongoing.

1.4.2.11 PRO 140_CD03 Study

PRO 140_CD03 study (open-label, two-arm comparator, 500 subjects, multi-center) seeks to evaluate the treatment strategy of using PRO 140 SC as long-acting single-agent maintenance therapy versus continuing combination ART for 48 weeks in virologically suppressed subjects with CCR5-tropic HIV-1 infection.

The first ~150 eligible subjects were enrolled to receive PRO 140 350mg SC weekly injection in a single-arm study. Subsequently, next ~150 subjects were randomized 1:1 to PRO 140 350mg (Group A) or PRO 140 525mg (Group B). An additional ~200 subjects will be randomized 1:1 to PRO 140 525mg (Group B) or PRO 140 700mg (Group C). This clinical study is currently ongoing.

1.4.2.12 PRO140_CD03 Extension Study

PRO 140_CD03 Extension study (open label, 300 subjects, multi-center) seeks to evaluate the long term efficacy, safety and tolerability of PRO 140 weekly injection as long-acting single-agent maintenance therapy versus continuing combination ART in patients infected with HIV-1. The study population includes treatment-experienced HIV-infected adult patients with CCR5-tropic virus who successfully completed PRO 140_CD03 study and continue to demonstrate HIV-1 viral suppression.

This clinical study is currently ongoing.

Table 1-1: Clinical Studies with PRO 140

Protocol Number	Phase	No. of Subjects (Planned/Analyzed)	Doses	Cell line used to make PRO-140	Subject Population	Comments
PRO 140 1101	1	20/20	Single 0.1, 0.5, 2.0, or 5.0 mg/kg	Sp2/0 myeloma	Healthy	Generally well tolerated; non-immunogenic; dose-dependent coating of CCR5; significant coating of CCR5 over placebo at 0.5, 2, and 5 mg/kg
PRO 140 1102	1	20/20	Either two or three doses totaling 200 or 350 mg respectively	CHO	Healthy	Generally well tolerated; drug derived from CHO cells well tolerated also; SC administration by Autoject® 2 better tolerated than manual injection
PRO 140 1103	1	15/14	Two doses, each of 350 mg	CHO	Healthy	More AEs associated with arm injection; trend of lower exposure in arm injections; thigh and abdominal administration preferred
PRO 140 1302	1b	40/39	Single 0.5, 2.0, or 5.0 mg/kg	Sp2/0 myeloma	HIV-1 positive	Generally well tolerated; antiviral suppression maintained for approx. 10 days with higher doses; favorable tolerability and potent, dose-dependent antiviral activity provide proof-of-concept
PRO 140 2301	2a	30/31	Single 5.0 or 10.0 mg/kg	CHO	HIV-1 positive	Generally well tolerated with no dose-limiting toxicities; potent antiviral suppression maintained for approx. 20 days when administered IV at 5 or 10 mg/kg. No dose-limiting toxicities at 10 mg/kg.
PRO 140 2101	2a	40/44	Three doses of 162 or 324 mg each	CHO	HIV-1 positive	Generally well tolerated, no drug-related SAEs or dose-limiting toxicity; antiviral activity was statistically significant; two-fold exposure at higher dose; single dose demonstrated favorable tolerability, and potent, long-acting, dose-dependent antiviral activity.

Protocol Number	Phase	No. of Subjects (Planned/Analyzed)	Doses	Cell line used to make PRO-140	Subject Population	Comments
PRO 140_CD01	2b	40/40	350 mg SC weekly dose for 12 Weeks of Monotherapy (total treatment duration 14 Weeks)	CHO	HIV-1 positive	Generally well tolerated, no drug-related SAEs, weekly dose demonstrated favorable tolerability, and potent, long-acting, dose-dependent antiviral activity. Results are pending publication.
PRO 140_CD01-Extension	2b	16/16	350 mg SC weekly monotherapy dose	CHO	HIV-1 positive	This clinical study is currently ongoing.
PRO 140_CD02	2b/3	50/52	350 mg SC or placebo + ART for 1 week, then 350mg SC weekly + OBT for 24 weeks	CHO	HIV-1 positive	This clinical study has been completed
PRO 140_CD02-Extension	2b/3	50/TBD	350 mg SC weekly + OBT	CHO	HIV-1 positive	This clinical study is currently ongoing.
PRO 140_CD03	2b/3	500/TBD	350 mg SC weekly dose for up to 48 weeks of monotherapy	CHO	HIV-1 positive	This clinical study is currently ongoing..

[figure not shown]
Protocol Number	Phase	No. of Subjects (Planned/Analyzed)	Doses	Cell line used to make PRO-140	Subject Population	Comments
PRO 140_CD03-Extension	2b/3	300/TBD	350 mg SC weekly monotherapy dose	CHO	HIV-1 positive	This clinical study is currently ongoing.

1.5 RATIONALE FOR DOSE SELECTION

The dose of 350 mg administered SC was chosen in light of a previous analysis suggesting that such a dose would be likely to provide maximal viral load suppression.

In studies with antiviral agents that block viral entry through the CCR5 receptor, there is a general consensus that in order to achieve robust antiviral effects and minimize the potential for drug resistance in combination therapy, the dose of drug should result in exposures that fall on the plateau of a Maximum Drug Effect (Emax) plot.

Figure 1-8: Emax analysis of antiviral data generated with IV and SC PRO 140.

The maximal viral load reduction was analyzed with regard to drug exposure for PRO 140. Figure 1-8 above shows this relationship. Analysis shows that PRO 140 350mg weekly dose is expected to fall on the plateau of the Emax plot.

The maximal change in HIV-1 viral load from baseline was determined at any point 59 days after initiation of therapy. To allow approximate comparisons between the IV and SC doses, the overall AUC observed for repeat SC doses was conservatively estimated by multiplying the measured AUC_{0-7d} by the number of doses administered. Viral load and AUC data were fit to an Emax equation: $E = E_{max} \times AUC / (AUC + AUC_{50})$. The orange diamond indicates projected data for three weekly 350 mg doses based on the mean exposure observed in the PRO 140 1103 study.

It is important to note that when larger proteins (MW> 10,000) are administered SC, they initially traffic through the lymphatic system. Uptake into the bloodstream occurs after the proteins reach the thoracic duct [Nishikawa M, 2005].

In addition, based on pharmacodynamic data from our prior SC and IV studies, maximum virologic suppression is expected to be achieved with trough concentrations that equal or exceed approximately 5 µg/mL.

Finally, the mean nadir reduction in viral load achieved with 3 weekly 324 mg SC doses (1.65 log₁₀) was similar to the mean nadir reductions observed with single 5 or 10 mg/kg IV doses (1.8 log₁₀ in each case), and higher viral load reductions are expected in the present study based on the use of the 350 mg CHO formulation. Overall, several lines of evidence indicate that maximum virologic suppression will be achieved with 350 mg weekly dosing in the present study.

Majority of subjects receiving 350 mg weekly SC dosing in monotherapy setting experienced virologic failure in CD01-Extension study. Review of PRO 140 clinical data to date with 350mg SC weekly dosing, suggests no evidence of emergence of viral isolates with reduced susceptibility to PRO 140, no altered viral tropism or anti-PRO 140 antibodies formation suggesting the most likely cause of viral rebound is inadequate dosing to fully cover CCR5 receptor populations. Based on pharmacologic modeling studies, we anticipate that the 700mg dose will result in a lower fraction of study participants with trough levels below that which will ‘uncoat’ a significant number of CD4 cells (i.e., less than a certain multiple of the IC50 or IC90 for PRO 140).

1.6 RISKS / BENEFITS ASSESSMENT

1.6.1 RISKS/DISCOMFORT TO SUBJECTS AND PRECAUTIONS TO MINIMIZE RISK

1.6.1.1 Risks associated with continuation of Failing Antiretroviral Treatment Regimen

As per standard of care, patients who failing on their ART remain on failing regimen while waiting for the results of HIV-1 drug resistance tests. A new drug regimen is constructed by the Investigator based on the subject’s resistance test results and treatment history. This duration corresponds with the screening phase of the study.

Once the results of resistance and tropism tests are available, the study treatment (PRO 140 700mg SC injection) will be added to the failing regimen for one week. After one week all subjects will receive PRO 140 SC injection and Optimized Background Therapy (OBT).

Addition of study treatment (PRO 140 700mg SC injection) to the failing regimen may not be effective in achieving a reduction in viral load for all subjects. Such cases could lead to an

increased risk of developing drug resistance, opportunistic infections and clinical progression of the disease.

1.6.1.2 Allergic Reaction

PRO 140 belongs to the monoclonal antibody class of drugs. Monoclonal antibodies are sometimes associated with allergic reactions (fatigue, diarrhea, fever, vomiting, headache, nausea, pain at the site of injection, low blood pressure, rash, itching, and chills) or flu-like reactions such as fever, chills, and aches. These events are usually of short duration if they occur at all. Severe allergic reactions, however, can be life-threatening. Although anaphylaxis has not been observed in prior trials of PRO 140, infusion of proteins always carries with it the theoretical risk for anaphylactic shock. Accordingly, whenever PRO 140 is initially administered to subjects, there should be available and in place the procedures required to manage anaphylactic shock.

1.6.1.3 Immune Response

Subjects who take PRO 140 or other monoclonal antibodies can also develop an immuneresponse to PRO 140 that may affect their ability to receive monoclonal antibodies, or to benefit from diagnosis or therapy with a monoclonal antibody in the future.

1.6.1.4 Pregnancy

Risks to unborn babies are unknown at this time; pregnant females will be excluded from this study. Females of childbearing potential must have a negative pregnancy test prior to enrollment. Both male and female patients and their partners of childbearing potential must agree to use appropriate birth control methods throughout the study duration (excluding women who are not of childbearing potential and men who have been sterilized).

1.6.1.5 Venipuncture

Blood sampling is required as part of the study protocol. Blood sampling carries a minimal risk of minor discomfort and the possibility of minor bruising at the site of the needle puncture and, rarely, the possibility of infection at the needle puncture site.

1.6.1.6 Risks to the Study Personnel and the Environment

The principal risk in the clinical setting is in the handling of needles that may be contaminated with HIV, or other human pathogens. Adherence to universal precautions for working with infectious agents will reduce the risk of exposure to these individuals. All bio-hazardous waste will be disposed of as stipulated by local, state, and federal regulations and in accordance with study site Standard Operating Procedures (SOPs).

1.6.1.7 Unknown Risks

As with all research there is the remote possibility of risks that are unknown or that cannot be foreseen based on current information.

1.6.1.8 Theoretical risk for increased severity of West Nile virus infection

Individuals who lack a functional CCR5 gene are at increased risk for severe infection by West Nile virus [Thompson, 2009]. Because of this, treatment with CCR5 co-receptor antagonists poses a theoretical risk for increased severity of West Nile virus infection. However, this concern is mitigated by several factors. First, no increased risk was observed for individuals who possess one functional and one non-functional CCR5 gene, indicating that an intermediate amount of CCR5 is sufficient for defense against West Nile virus [Thompson, 2009]. Second, use of CCR5 co-receptor antagonists is unlikely to completely abrogate CCR5 function, and there has been no association reported to date between CCR5 co-receptor use and severe West Nile virus. Additionally, PRO 140 weakly antagonizes the natural activity of CCR5 and thus is less likely to adversely affect immune function. Furthermore, this has not been established to be a risk with maraviroc, the anti-CCR5 drug already FDA-approved for the treatment of HIV.

Collectively, the experience with both IV and SC, simulation modeling and the recent confirmation that a higher concentration of PRO 140 synthesized using a highly efficient CHO cell line can be conveniently and safely administered has resulted in the design of the current study.

1.6.2 INTENDED BENEFIT FOR SUBJECTS

This study provides an opportunity for subjects to have supervised once weekly SC treatment with PRO 140 in addition to an optimized and simplified ART regimen. Subjects participating in the present short term combination therapy study for 25 weeks will contribute to the development of a drug which has the potential to become a treatment option for them and others in the future.

2 STUDY OBJECTIVES

The primary objective is to assess the efficacy, clinical safety and tolerability parameters of PRO 140 in reducing HIV-1 viral load in patients on their current ART (failing regimen) during the 1-week treatment period, and in combination with Optimized Background Therapy during the subsequent 24-week treatment period.

The primary efficacy endpoint is proportion of participants with ≥ 0.5 log10 reduction in HIV-1 RNA viral load from baseline at the end of the initial 1-week treatment period.

The secondary efficacy endpoints will be proportion of participants with ≥ 1 log10 reduction in HIV-1 RNA viral load from baseline at the end of the initial 1-week treatment period, mean change from Baseline in HIV-1 RNA levels (log10 copies/mL) at the end of the initial 1-week treatment period, percentage of participants achieving HIV-1 RNA < 400 copies/mL at week 25, percentage of participants achieving HIV-1 RNA < 50 copies/mL at week 25, mean change from Baseline in HIV-1 RNA levels (log10 copies/mL) at week 25, mean change from Baseline in CD4 cell count at the end of 1-week treatment period, and mean change from Baseline in CD4 cell count at week 25.

Safety assessments include evaluation of emergence of Dual/Mixed (D/M)- and CXCR4-tropic virus in patients who had exclusive CCR5-tropic virus at study entry, tolerability of repeated subcutaneous administration of PRO 140 as assessed by study participants (using Visual Analogue Scale) and by investigator—evaluation of injection site reactions, frequency of treatment-related adverse events resulting in study drug discontinuation, frequency of Grade 3 or 4 adverse events and frequency of treatment-emergent serious adverse events.

3 STUDY DESIGN

This is a multi-center, two part study, designed to evaluate the efficacy, safety and tolerability of PRO 140 in conjunction with existing ART (failing regimen) for one week and Optimized Background Therapy (OBT) for 24 weeks respectively. The patient population for this trial are treatment-experienced patients with CCR5-tropic virus and demonstrates evidence of HIV-1 replication despite ongoing antiretroviral therapy with documented genotypic or phenotypic resistance to ART drugs within three classes, or two drug classes with limited treatment options.

The study is divided into four phases: Screening, Baseline, Treatment, and Follow-up.

Screening Phase begins with signing of Informed Consent and lasts up to 6 weeks. Subject will enter the Treatment Phase as soon as HIV-1 viral tropism, genotypic and/or phenotypic resistance results are available for review by Investigator.

The Baseline visit is to confirm HIV RNA continues to meet eligibility and will be conducted one week prior to the first treatment.

The Treatment phase is divided into two parts:

- **Part 1:** One-week treatment period consisting of PRO 140 along with existing ART (failed regimen).
- **Part 2:** 24-week treatment period consisting of PRO 140 along with Optimized Background Therapy (OBT)

All subjects will continue taking their existing ART (failed regimen) during the Screening Phase and first week of the Treatment Phase (Part 1). After Treatment Phase Part 1, all subjects will enter the 24-week treatment period (Part 2). During this period, all subjects will receive PRO 140 SC injection and OBT.

Study participants will be regularly monitored for viral load following initiation of PRO 140, and will cease weekly study treatment injections should they experience treatment failure.

Subjects who experience treatment failure at any point during Treatment Phase Part 2 will undergo the Treatment Failure (TF) Visit assessments and will be followed up every 4 weeks until viral suppression is achieved (i.e., plasma HIV-1 RNA levels below level of detection) or up to a maximum of 6 months after cessation of therapy if the treating physician does not feel that there is an antiretroviral regimen that will regain full viral suppression. Subjects who do not experience treatment failure, will be followed up every 2 weeks for a total of 4 weeks.

Note: Subjects who are currently enrolled and receiving 350 mg dose will have the option to move to the 700 mg dose for the remainder of their participation in the trial.

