
Treatment Phase (25 weeks ± allowed windows):
 
The Treatment Phase is divided into two parts:
 
 • Part 1: 1-week treatment period consisting of PRO 140 along with existing ART (failing regimen) • Part 2: 24-week treatment period consisting of PRO 140 along with OBT 
The injectable study treatment (PRO 140) will be administered starting at T1 visit and weekly thereafter:
 
 ○ by a qualified medical professional (MD, DO, PA, LPN, LVN, NP, RN, or CMA if permitted by state law) or ○ self-administered by subjects 
Subjects will receive PRO 140 700 mg administered subcutaneously once per week.
 
Note: Subjects who are currently enrolled and receiving 350 mg dose will have the option to move to the 700 mg dose for the remainder of their participation in the trial.
 
Note: Study treatment injections at T1, T2, T3, T7, T11, T15, T19 and T23 must be administered at clinic. The remaining study treatment injections may be self-administered by subjects outside the clinic.
 
Part 1: One-week treatment period [PRO 140 + existing ART]
 
Part 1 of treatment phase begins with an evaluation of results of laboratory samples collected at the Screening Visit. All subjects who fail to meet eligibility criteria will be considered screen failures and exit the study without further evaluation. Subjects who meet all eligibility criteria, as per data gathered from Screening Visit, will be enrolled and receive PRO 140 for one week (Table 0-1). A visit to confirm HIV RNA continues to meet eligibility will be conducted one week prior to the first treatment.
 
Table 0-1: One-week period [PRO 140 + existing ART]
	

Name of Sponsor: CytoDyn, Inc.				
Name of Study Product: PRO 140 (Humanized monoclonal antibody to CCR5)				
Protocol Number: PRO 140_CD02_OpenLabel	Therapeutic Indication: Human Immunodeficiency Virus Type-1 (HIV-1) Infection			
Study Drug	Dosage Form	IP concentration	Dosing Frequency and Amount	Route of Administration
PRO 140	Parenteral solution	175 mg/mL	2 injections of PRO 140 (2 X 2 mL/inj.) at T1 visit	SC injection

Part 2: 24-week treatment period [PRO 140 + OBT]

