8 STATISTICAL CONSIDERATIONS

This section presents general information about statistical considerations and concepts such as statistical power, sample size, and a brief discussion on analysis methodology, as well as some data conventions. Detailed descriptions of the statistical analysis methods and data conventions that will be used in this study will be in a separate document; i.e., the Statistical Analysis Plan (SAP).

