8.1 TREATMENT GROUPS

This is an open label study. All eligible subjects will receive study treatment within 6 weeks of Screening Visit, followed by weekly subcutaneous injections of study treatment for up to 24 weeks.

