8.6 GENERAL STATISTICAL CONSIDERATIONS

8.6.1 Analysis Populations

8.6.1.1 Intent-to-Treat Population

The Intent-to-Treat (ITT) population is defined as the set of subjects who are enrolled and have received at least one dose of PRO 140.

Subjects who discontinue from the study prior to their first post-baseline assessment will be included in the ITT population and analyzed as non-responders in the primary safety analysis.

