8.6.3 Prognostic Factors/Covariates

There are no pre-planned covariates analyses of the data from this study.

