8.7.4 Efficacy Analysis

8.7.4.1 Primary Analysis

The primary analysis will be conducted on the ITT population.

All data from the primary and secondary endpoints will be summarized and tabulated according to the variable type:

- Continuous data summaries will include:
Number of observations, mean, standard deviation, median, and minimum and maximum values.
- Categorical data summaries will include:
 - Frequency counts and percentages.

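### Subjects start on 350 mg or 700 mg, yet Section 8 defines no dose groups, so unless the SAP separates them the week-1 proportion describes an unstated dose mix; the delivered-volume passages also conflict

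*Protocol*

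**What the plan says.** **Dose.** The synopsis (Treatment Phase) states: "Subjects will receive PRO 140 700 mg administered subcutaneously once per week". A note there and in Section 3 adds: "Subjects who are currently enrolled and receiving 350 mg dose will have the option to move to the 700 mg dose". The move lasts for the rest of the subject's time in the trial.

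**Groups and analysis sets.** Section 8.1 is headed Treatment Groups but names no group and no dose: "All eligible subjects will receive study treatment within 6 weeks of Screening Visit". The ITT population (8.6.1.1) is "the set of subjects who are enrolled and have received at least one dose of PRO 140", at whatever dose. Section 8.7.4.1 runs the primary analysis on that set and says: "All data from the primary and secondary endpoints will be summarized and tabulated according to the variable type". Section 8.7.4.2 repeats the method on the per-protocol subset. Section 8.7.5.1 summarises treatment-emergent adverse events by treatment group, a term the protocol does not define.

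**Deferral.** Section 8 opens by saying: "Detailed descriptions of the statistical analysis methods and data conventions that will be used in this study will be in a separate document". That document is the SAP, which is not at hand.

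**Delivered volume.** Section 4.3.1, parts of Section 6.1, the syringe labels in Section 6.2 and Section 6.4 describe two injections or syringes of 1 mL. Tables 0-1, 0-2, 4-3, 4-4, 6-1 and 6-2, and another sentence of Section 6.1, describe two injections of 2 mL. Sections 6.1 and 6.4 also allow 700 mg as four 1 mL injections for subjects with low body fat. Section 6.1 assigns one kit per visit, and a kit holds two vials of about 1.4 mL.

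**The concern.** The trial is meant to supplement the data for a licence application (8.3), and its current regimen is 700 mg. A reader of the headline week-1 proportion needs to know which dose it describes. If starters on the two doses are summarised together, the figure depends partly on how many subjects happened to enrol before the dose changed, a number the protocol does not give.

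From week 2 onward there is a second layer. Subjects who began on 350 mg may choose whether to move up. Those who move are self-selected, and their later viral loads and adverse events arise under both doses. A safety table by an undefined treatment group leaves open where those subjects and events belong.

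The volume conflict matters here because a dose group can be assigned only if the dose given is clear.

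**Working it through.** **1. Who is in the analysis set.** Part 1 consists of one administration, at T1 (Table 4-3). A subject already receiving 350 mg has therefore had the T1 dose at 350 mg. The ITT set then contains three kinds of subject:

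| Path | Dose behind week 1 | Dose behind week 25 and safety |
|---|---|---|
| 350 mg throughout | 350 mg | 350 mg |
| 350 mg, then 700 mg by choice | 350 mg | both |
| 700 mg throughout | 700 mg | 700 mg |

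The week-1 endpoint has two starting doses and is untouched by switching. The week-25 and safety summaries have all three paths. Nothing in 8.1, 8.6.1.1, 8.7.4.1 or 8.7.5.1 separates them.

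**2. Effect on the week-1 proportion.** The planned size, up to 25 or as many as can be enrolled by the licence application, rests on clinical judgement, so there is no power calculation to reproduce. Let N be the number of subjects, k the number started on 350 mg, and p350 and p700 the two response proportions. Then

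pooled = [k × p350 + (N − k) × p700] / N, so p700 − pooled = (k/N) × (p700 − p350).

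The protocol gives neither k nor the response proportions. Taking N = 25 and an assumed gap of 10 points, the shift is (k/25) × 10:

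| k | 1 | 5 | 10 | 15 | 20 | 24 |
|---|---|---|---|---|---|---|
| Shift (points) | 0.4 | 2.0 | 4.0 | 6.0 | 8.0 | 9.6 |

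If the gap is 0, the shift is 0 for every k. With assumed proportions of 0.50 and 0.70, the pooled value is 0.70 at k = 0, 0.62 at k = 10 and 0.54 at k = 20.

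**3. Does the protocol expect a gap?** Section 1.5 points both ways. It places 350 mg weekly on the plateau of the Emax curve, which argues for no gap. It also names inadequate dosing as the likeliest cause of rebound at 350 mg. That statement concerns longer monotherapy and is weak support for a difference after one week.

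**4. Delivered dose at 175 mg/mL.**

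- Two 1 mL injections: 2 × 1 × 175 = 350 mg.
- Two 2 mL injections: 2 × 2 × 175 = 700 mg.
- Four 1 mL injections: 4 × 1 × 175 = 700 mg.
- One kit: 2 × 1.4 × 175 = 490 mg, and 490/700 = 70%.

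Section 6.1 alone contains the 1 mL draw, the two 2 mL injections and the 1.4 mL vials. The protocol does not say that the 1 mL passages apply only to subjects on 350 mg.

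**5. Precision if the groups are shown.** At an assumed 80% response, exact (Clopper-Pearson) 95% intervals would be: 20/25, 59% to 93%; 12/15, 52% to 96%; 8/10, 44% to 97%; 4/5, 28% to 99%.

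**The case against.** The strongest reply is that table layout belongs in the SAP. Section 8.7.4.1 prescribes summary statistics by variable type. It is silent on columns and does not order a single pooled one, so the SAP may well show dose columns, and by-subject listings are promised in any case. This stands, and the point is therefore conditional on the SAP. It does not clear the protocol: a section headed Treatment Groups does not reflect the design in Section 3, and 8.7.5.1 uses a term that has no definition. Reading it as one open-label group is natural, but the protocol does not say so, and that reading would combine the doses for safety as well.

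Some further inferences are not supported:

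- **That the protocol rules out reporting by dose.** Section 8.6.3 says "There are no pre-planned covariates analyses of the data from this study", but tabulating by dose is not a covariate analysis.
- **That Section 8 defines its study treatment as 700 mg.** Section 1.6.1.1 says "the study treatment (PRO 140 700mg SC injection) will be added to the failing regimen for one week", but that is a risk paragraph and carries little weight for Section 8.
- **That the primary result is biased by switching or by a known amount.** Switching cannot alter the week-1 result of a subject already dosed at 350 mg, and the size of any shift is unknown.
- **That subjects were given the wrong amount.** The documents show conflicting instructions, not what was administered.

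It is also fair to say that the volume conflict is a separate defect. It would exist if every subject had started on 700 mg, and it adds nothing to the case that Section 8 is incomplete.

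**Conclusion.** The point holds in a limited form. The protocol provides for two starting doses and an optional switch, and its statistical section distinguishes none of them. Unless the SAP does so, the week-1 proportion describes an unstated mix of starting doses, and the week-25 and safety summaries also include self-selected switchers.

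The size cannot be found from the protocol. It is 0.4 points per 350 mg starter for each assumed 10-point gap at N = 25, and it is zero if the two doses perform alike at week 1. The planned analyses are descriptive, so no error rate or power is affected.

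The contradiction in delivered volume (350 mg, 700 mg, or a 490 mg kit) is firm. It rests on the text alone and needs no assumption. I take no view on which volume or dose is right.

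**What to change.** 1. Reconcile the volume, vial and kit passages (Sections 4.3, 4.3.1, 6.1, 6.2 and 6.4, and the synopsis tables) with each other and with the stated dose, including the four-injection option.
2. In 8.1, define groups by starting dose at T1.
3. Report the week-1 endpoints by starting dose, and label any pooled figure as mixed-dose.
4. Report the week-25 endpoints descriptively by starting dose, with switchers identified.
5. In 8.7.5.1, replace the undefined term with one stated safety grouping: 350 mg only, 350 mg to 700 mg, and 700 mg only, each with its own subject denominator. Show dose at onset in the adverse-event listing.
6. Take dose at onset from the dose recorded at each administration. The accountability records in 6.3 and 6.5 show what was dispensed. Only 8 of the 25 injections must be given in the clinic, so up to 17 may be self-administered elsewhere, and dispensed is not the same as administered.

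The cost is some wording in Section 8, extra table columns and, if it is not already captured, a dose entry per administration. The real downside is smaller denominators: at 80% response, the interval widens from 59% to 93% with 25 subjects to 44% to 97% with 10.
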